5.0 STUDY DESIGN

This study is open-label controlled randomised, 1:1, multicentre strategic trial. Patients will be randomised to immediate vs delayed switch, with randomization allocation arranged to minimize differences between treatment groups with respect to country.

5.1 Study population:

HIV positive women who are in the peri-menopausal period or those within 10 years post menopause to capture those with greatest risk of BMD loss. As menopause typically occurs earlier in HIV + women we include those aged 40 - 60 years.³² They must be on a cART regimen containing TDF/FTC with HIV RNA <50 c/ml for at least 6 months.

5.2 Intervention:

1. Immediate switch of TDF/FTC to TAF/FTC while maintaining the third ARV agent.
2. Delayed switch of TDF/FTC to TAF/FTC at 48 weeks while maintaining the third ARV agent.

5.3 Randomization

A computer-generated randomization list will be prepared prior to study onset by a statistician/programmer at the CIHR Canadian HIV Trials Network. Randomization will be stratified by country. Site coordinators will each be given a personal code through which they

can access the web randomization system. When a site coordinator has identified an eligible, consenting participant, s/he will access the web page, register the participant and indicate non-nominal information linked to the participant. The computer will record date and time of the transaction, the participant information and allocation, which will be issued to the coordinator.

5.4 Primary endpoint:

Comparison of the immediate vs delayed group in the % change from baseline in BMD at the lumbar spine at week 48.

5.5 Secondary endpoints

We will compare changes between the immediate and delayed group from data collected at screening or baseline and weeks 48 and 96.

% change from baseline in BMD at lumbar spine at 96 weeks

% change from baseline in BMD at hip at 48 weeks

% change from baseline in BMD at hip at 96 weeks

Changes in Bone architecture as determined by Trabecular bone scan (TBS)²⁵ and HRpQCT²⁶

Changes in 10 year fracture risk determined by country specific FRAX calculator³³

% with undetectable viral load HIV-1 RNA as per current assays. (This **may be** < 50/ml, < 40/ml or viral load not detected)

Change from baseline in geriatric functional measures: frailty, performance and balance

Change from baseline in muscle quality: Sarcopenia – grip strength measured by a Dynamometer and fat free mass measure (from the DXA)

Change from baseline in lipid values and Framingham cardiovascular risk scores

Changes in renal tubular and glomerular function: eGFR, Cr, urine alb/cr and protein/cr, glucosuria

Safety (clinical and laboratory adverse events)

Changes in biomarkers of inflammation, coagulation and bone metabolism

Tolerability (EuroQoL questionnaire)

5.6 Justification of Endpoints:

Primary Endpoint: BMD assessment with dual energy x-ray absorptiometry (DXA) is well established for the diagnosis of osteoporosis and for fracture risk assessment in postmenopausal women⁷. For BMD measurements to be clinically useful, they are expressed in comparison with

established normative databases. BMD is expressed as a numerical value (g/cm²). Change in BMD is considered a valid intermediate end point for efficacy of fracture risk reduction⁷. To inform the site and timing of the primary endpoint, data from studies of bisphosphonates (a major therapy for osteoporosis) was used in which the increase in BMD is greatest at the lumbar spine, with one half of the gain of BMD achieved within 6–12 months followed by a lower increase over subsequent years³⁴

Secondary Endpoints: New imaging modalities are increasingly incorporated into studies of osteoporosis to gain more detailed information on bone strength.

Trabecular bone score (TBS) is a recently-developed analytical tool that performs novel measurements on lumbar spine DXA images, and captures data relating to trabecular microarchitecture²⁵. Low TBS is consistently associated with an increase in both prevalent and incident fractures that is partly independent of both clinical risk factors and BMD. TBS has predictive value for fracture independent of probabilities using the FRAX® algorithm.³³

High-resolution peripheral quantitative computed tomography (HRpQCT) is a new method that can determine both bone geometric parameters (such as cortical thickness, trabecular thickness, trabecular separation and trabecular number) and BMD (such as total, cortical and trabecular volumetric BMD). This technology offers a non-invasive method to gain unique insights into bone microarchitecture that are not obtainable using routine DEXA and can provide additional 3-dimensional information about bone architecture that is associated with fracture, even among those with similar DXA results.²⁶ Given limited availability it will only be performed at selected participating sites.

As BMD does not add details on overall function or provide data on clinical outcomes, we include a broader geriatric assessment of study participants including:

1. **Sarcopenia** with a combined definition of fat free mass measure (from the DXA) and muscle grip strength obtained with a handheld dynamometer³⁵
2. **Frailty** measured with some components from a Frailty Index.
3. **Short performance physical battery test (SPPB)** to assess balance, and walking speed³⁷
4. **Fall frequency**, assessed using self-administered questionnaire validated in the 2008 National Health Interview Survey Dizziness and Balance Supplement.³⁸

Increasingly **biomarkers** are studied with the goal to identify surrogate markers for use in interventional studies where clinical endpoints are less frequent. Many of the comorbidities seen with aging in HIV may be a consequence of persistent immune activation and inflammation despite control of HIV replication. Therefore we propose to collect samples to enable further analysis of putative biomarkers to be correlated with BMD changes.^{4, 39-41}

1. **Biomarkers of bone formation and resorption**- to include - C-terminal cross-linked telopeptide of type I collagen (CTX) procollagen 1 N terminal extension peptide (P1NP) , vitamin D, Ca ⁴¹
2. **Biomarkers of immune activation and inflammation** which could include- (CD38+CD8+ and CD4+T cells), inflammatory cytokines (IL-1b, IL-6, MCP-1, TNF), endothelial activation (sICAM-1, sVCAM-1) and the acute phase reactant hsCRP. ³⁹⁻⁴⁰We are currently conducting a systematic review of the published literature to inform the optimal measures... Panels of the most appropriate measures will be conducted at study end.

The second major reported toxicity of TDF is renal insufficiency ⁴²⁻³. As improvements are reported with TAF, **measures of renal glomerular and tubular function** are included as secondary outcomes. TDF has a more favourable lipid profile than TAF, and we will also assess **lipid parameters and cardiovascular risk scores**.

6.0 ELIGIBILITY CRITERIA

6.1 Inclusion Criteria – all criteria must be met

1. Biological female aged 40 – 60
2. Documented HIV-1 infection **by means of any one of the following:**
 - i. **Documentation of HIV diagnosis in the medical record by a licensed health care provider;**
 - ii. **OR HIV-1 RNA detection by a licensed HIV-1 RNA assay demonstrating >1000 RNA copies/mL;**
 - iii. **OR any licensed HIV screening antibody and/or HIV antibody/antigen combination assay confirmed by a second licensed HIV assay such as a HIV-1 Western blot confirmation or HIV rapid Multispot antibody differentiation assay.**
3. Peri-menopausal or within 10 years of menopause (based on history history).
4. Signed Informed Consent Form and willing to comply with the protocol.
5. Receiving a cART regimen containing a ritonavir boosted PI (darunavir, atazanavir, lopinavir,) or an NNRTI (efavirenz, nevirapine or rilpivirine) or an integrase inhibitor (dolutegravir, raltegravir or elvitegravir) in combination with TDF-FTC for > 24 weeks.
 - i. Participants on a single tablet regimen containing TDF/FTC are able to participate as long as they meet the virologic suppression criteria.
 1. For those who are on elvitegravir/cobicistat/tenofovir disoproxil fumarate/emtricitabine (EVG/c/TDF/FTC), they will either remain on their current regimen or switch to elvitegravir/cobicistat/tenofovir alafenamide/emtricitabine (EVG/c/F/TAF).

2. For those who are on rilpivirine/tenofovir disoproxil fumarate/emtricitabine (RPV/TDF/FTC), they will either remain on RPV/TDF/FTC or switch to rilpivirine/tenofovir alafenamide/emtricitabine (RPV/F/TAF).
3. For those on other single tablet regimens, if no component needs to be changed they will need to switch to TDF/FTC and the third agent in the STR as separate tablets prior to randomization. If the third agent needs to be changed they will need to switch to TDF/FTC plus the new third agent and show continued evidence of viral suppression for one month prior to randomization. For example: those on atripla would need to switch to TDF/FTC plus efavirenz and be randomized immediately or switch to TDF/FTC plus dolutegravir and remain suppressed for one month before randomization.
 - ii. Those who are on more than 3 agents are eligible provided they meet these criteria.
6. Stable viral suppression (plasma HIV-RNA<50 copies/mL for > 24weeks). Single viral blip <500 copies/mL allowed if re-suppresses.
7. If of childbearing potential, is using effective birth control methods and is willing to continue during the trial.
8. Women will be assessed for vitamin D and calcium dietary intake; if inadequate for age, supplements will be recommended.

6.2 Exclusion Criteria - if any are present the participant cannot be included

1. HIV-2
2. High 10-year fracture risk at screening (> 20%) based on country specific FRAX
3. Current treatment with active bone medications- bisphosphonates, denosumab, calcitonin, raloxifene, teriparatide, stontrium
4. Current use of systemic steroids (inhaled steroids permitted) or chemotherapeutic agents
5. Acute viral hepatitis
6. Chronic hepatitis C with AST and/or ALT $\geq 5 \times$ ULN or expected to require HCV treatment during the trial period.
7. Any investigational ARV within 30 days.
8. Dialysis or renal insufficiency (creatinine clearance < 50ml/min)
9. History of decompensated liver disease (AST or ALT $\geq 5 \times$ the upper limit of normal (ULN) or ALT $\geq 3 \times$ ULN and bilirubin $\geq 1.5 \times$ ULN with > 35% direct bilirubin), or the presence of ascites, encephalopathy, coagulopathy, hypoalbuminemia, esophageal or gastric varices.
10. Pregnant or breastfeeding

11. Screening blood result with any grade 3/4 toxicity according to Division of AIDS (DAIDS) grading scale, except: asymptomatic grade 3 amylase, CPK, or lipid elevation.
12. Any condition (including illicit drug use or alcohol abuse) or lab results which, in the investigator's opinion, interfere with assessments or completion of the trial.

7.0 STUDY EVALUATIONS AND PROCEDURES

7.1 Clinical Evaluations

Once a candidate for screening has been identified, study details will be carefully discussed with the potential participant. The participant will be asked to read and sign the approved informed consent form prior to any assessments being performed.

Medical history, documented HIV test results, and demographic information will be obtained at the screening visit. Data will be collected on age, race, HIV risk factor, smoking history, exercise habits, prior fractures, calcium and vitamin D intake, illicit drug use, alcohol, steroid use, ARV history, past medical illness, medications, menstrual history, obstetrical history, weight, body mass index. The FRAX calculator will be used to estimate 10 year fracture risk.

Routine investigations will include viral load, CD4, haematology, biochemistry, lipids, endocrinology, renal monitoring. These are investigations that are typically performed as part of standard of care at 3 month intervals and will not be done specifically for study purposes but the data will be collected and recorded. Hepatitis B and C status will be recorded.

A complete physical exam, including vital signs will also be performed at the screening visit. A brief physical exam, including vital signs, will be performed as per site local practices at subsequent visits. Information pertaining to medication review, and adverse events will be collected as indicated in Table 1 (Appendix A).

Information regarding the antiretroviral regimens including time of starting ART and type of drugs will be recorded. While on the study, ART switching, adherence to ART or stopping ART for any reasons will also be documented.

Sarcopenia will be determined with a combined definition of fat free mass measure (from the DXA) and muscle grip strength obtained with dynamometer

Short performance physical battery test (SPPB) will be performed to assess walking speed and balance.

7.2 Participant Identification Number Assignment

Participant Identification (ID) numbers will be assigned sequentially to each participant who is eligible to participate in the study. Participants who are not eligible for the study will not be assigned a Participant ID Number. The Participant ID Number will consist of a three digit centre number and a three digit number according to chronological order of entry at each centre. Details for assigning Participant ID Numbers will be provided in the Operations Manual. Log(s) should be completed by each site to capture all participants who have consented and who have been assigned a participant identification number. If a patient discontinues from the study the Participant ID Number will not be reused.

The Participant ID Numbers will be used for identification of participants in the source documentation, CRFs, and laboratory samples. This will ensure that participant data and laboratory samples leaving the study sites will be identified and tracked.

7.3 Imaging

Participants will complete DXA scans at the local site. Specific software will be used to calculate the trabecular bone score at selected sites. Participants enrolled at selected participating sites will undergo HRpQCT.

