8.0 STUDY VISITS

8.1 Screening visit:

The screening visit is anticipated to require 1-2 hours of the participant's time.

During this visit the following will take place:

- Informed Consent
- Assign Participant ID Number
- Demographic Information
- Medical History
- Physical Exam

- Calcium and Vitamin D intake assessment
- FRAX Score determined by country specific FRAX calculator
- Framingham Cardiovascular Risk Score
- Vital Signs including height, weight and determination of BMI
- HIV Viral load (within 1 month of screening date)
- Serum Pregnancy test and FSH (if post-menopausal)
- Hepatitis B and C (only if not previously tested)
- Hematology and biochemistry: CBC with differential and liver profile (AST, ALT, serum creatinine, Urinalysis, GFR, Urine albumin/creatinine, urine protein/creatinine) (within 1 month of screening date)
- Medication Review
- Review of Eligibility Criteria
- Dexa scan will be scheduled before baseline visit. (Dexa scan should be completed prior to Randomization.).

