8.3 Follow-up Visits for Participants

These will occur at weeks 4, 12, 24, 36, 48, 52, 60, 72, 84 and 96. At weeks 4, 12, 24, 36, 52, 60, 72, and 84, the participants will have routine investigations as per the study site, and will complete targeted physical exams. **Complete** physical exams, labwork as outlined in the schedule of Assessments on pages 25 – 26, and FSH (if premenopausal) will be required at weeks 48 and 96. Adverse events will be captured at each study visit as will any changes in clinical conditions or medications. Pill counts of returned study drug except week 52 will also be captured. The accepted windows around study visits are +/- 7 days. The procedures will last about 60 minutes.

If they agree, participants will continue to be followed even if they decide to stop the study medication

At weeks 48 and 96 all participants will complete the study imaging, collection of plasma specimens for marker banking, quality of life questionnaires, FRAX score as determined by country specific FRAX calculator, Framingham cardiovascular risk score, and geriatric measures as above. The additional procedures will last

approximately 30 minutes plus imaging time. The imaging is to be scheduled within 4 weeks of these visit dates.

Drug dispensation will be done every 3 months during the regular visits at W0, 12, W24, W36, W48, W60, W72, and 84. At week 48, all participants will receive open label TAF/FTC.

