8.4 Final Study Visit (Week 96 +/- 14 days)

The duration of the study is 2 years per participant. Participants will be recruited during the first year of the study and will be followed for 96 weeks. The final visit will be the participant's last follow-up visit and the following assessments will take place:

- Complete Physical Exam
- Vital Signs
- Hematology and biochemistry: CBC with differential and liver profile (AST, ALT), serum creatinine, calcium, phosphate, Urinalysis, GFR, Urine albumin/creatinine, urine protein/creatinine, lipids- cholesterol, LDL, HDL, TG, glucose. CD4/CD8
- Urine pregnancy test and FSH (if premenopausal)
- HIV Viral Load
- Research Blood Sample
- Questionnaires- quality of life, adherence, falls, balance
- Frax Score determined by country specific FRAX calculator
- Framingham Cardiovascular Risk Score
- Medication review: ART and Other Concomitant Medications
- Imaging as per study site: DXA, TBS, HRpQCT
- Geriatric assessment, with questionnaires (frailty, quality of life, balance, falls), dynamometer, performance walking test.

To collect any information on potential adverse event reaction, patients will be called 4 weeks after their last visit at 96 weeks +/- 7 days.

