13.0 DETAILS OF STATISTICAL ANALYSIS

13.1. Sample size considerations

128 women, 64 per group, are required to detect a difference of 1% in the annual change in spine BMD at 48 weeks between those randomized to immediate switch to TAF/FTC vs those randomized to delayed switch to TAF/FTC with a two sample t test, assuming a standard deviation (SD) of 2%, 80% power and a significance level of .05. The difference of 1% is believed to be a clinically important difference to detect. The expected rate of loss in BMD in peri- and post-menopausal women is 1-3% per year.

The SD in the % change in BMD was estimated from several studies of BMD in HIV+ individuals. Yin et al ⁴⁹ compared longitudinal changes in BMD in pre and post-menopausal HIV+ and uninfected women in two separate cohorts. In the premenopausal period annual % decrease in BMD was not different in HIV+ and HIV- at the lumbar spine (LS) (-0.8 +/-2.1% vs 0.4 +/-1.9%, p=.20) and remained similar after adjusting for traditional risk factors. In the postmenopausal period annualized rates of bone loss adjusted for baseline BMD were higher in HIV+ women by 2.4 fold at the LS (-1.2 vs -0.5 %, p<.00009). In a randomized study, where participants were 90% men, mean age 40, switching from TDF to TAF containing regimens

showed a statistically significant increase in BMD (median(IQR) + 1.79 % (-.22%, 3.38%)vs 0.28% loss(-2.25,1.5%), p<.001).²¹ Another study (85 % men, median age 49) showed a mean increase in BMD of 1.5% at 48 weeks with a switch from TDF to TAF compared to a .2% loss in those continuing TDF. ²⁹A third study in persons with impaired renal function switching from a TDF to TAF containing regimen resulted in a mean increase in BMD of 2.29% at the spine and 1.47% increase at the hip.²²

13.2 Primary analysis:

Generalized linear mixed models (GLMM) will be used to estimate the effect of immediate vs delayed switch from TDF/FTC to TAF/FTC on the percent change in BMD at the spine at 48 weeks.

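### The primary endpoint is a locally acquired spine DXA in an open-label trial, and the plan neither masks follow-up acquisition or analysis nor keeps each woman on one scanner

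*Combined protocol and SAP*

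**What the plan says.** Section 5.0 describes the design: "This study is open-label controlled randomised, 1:1, multicentre strategic trial". Section 5.4 gives the primary endpoint: "Comparison of the immediate vs delayed group in the % change from baseline in BMD at the lumbar spine at week 48".

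Section 7.3 has three sentences. The one on DXA is "Participants will complete DXA scans at the local site"; the other two cover trabecular bone score software and HRpQCT at selected sites. Section 8.4 repeats the delegation for the final visit: "Imaging as per study site: DXA, TBS, HRpQCT".

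The remaining text on DXA concerns timing. For baseline, section 8.1 says "Dexa scan should be completed prior to Randomization", and a footnote to the schedule in 8.7 places the scan before the baseline visit. For weeks 48 and 96, section 8.3 says "The imaging is to be scheduled within 4 weeks of these visit dates".

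No section states who analyses the scans or where, masks that person or the technologist, requires the same scanner or software for each woman, asks for the scanner to be recorded, or says what happens if it changes. Randomisation (5.3) is stratified by country only, and the model in 13.2 adjusts for country, with an optional term for hormone replacement. An Operations Manual is cited for ID numbers, the toxicity table and CRF completion, but not for DXA.

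**The concern.** Two separate risks follow, and they act differently.

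**Bias.** Site staff know the arm after randomisation. If the person who positions the woman or analyses the spine image at week 48 also knows it, choices about positioning, region placement or excluded vertebrae could lean with the arm. Such an error enters the change score directly, and a larger sample does not remove it. The sensitivity analyses in 13.7 deal with missing data, not with measurement.

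**Noise.** Percent change within a woman removes a scanner's proportional calibration only if the scanner and software stay the same. If they change between baseline and week 48, the offset between machines is added to her change. The country term cannot absorb this, and central data checks cannot detect it if the scanner is not recorded.

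The target is a difference of 1 percentage point, so modest shifts of either kind could matter.

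**Working it through.** **Inputs from section 13.1.** Difference 1%, SD of change 2%, power 80%, significance level 0.05, 64 per group: "128 women, 64 per group, are required to detect a difference of 1% in the annual change in spine BMD at 48 weeks", "with a two sample t test". Sidedness is not stated. From 13.7: 10% dropout before week 48.

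**Step 1: reproduce the plan's figure.** Standardised difference = 1/2 = 0.5. A two-sided two-sample t test at 0.05 with 80% power needs 63.8, so 64 per arm and 128 in total. The plan's figure reproduces. A one-sided test would need only about 50 per arm, so the plan's calculation is two-sided. Power at exactly 64 per arm is 80.1%. With 10% dropout (64 × 0.9 = 57.6, about 58 per arm) it is 76.1% before any added noise.

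**Step 2: noise from scanner changes.** The documents give neither the share of women who change scanner (f) nor the SD of the resulting offset (s); both are assumptions here. If offsets average zero and are independent of arm, the SD of change becomes √(2² + f·s²). Power is from the noncentral t with difference 1%.

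| Share f | Offset SD s | SD of change | Power, 64 per arm |
|---|---|---|---|
| none | – | 2.00% | 80.1% |
| 5% | 1% | √(4 + 0.05×1) = 2.01% | 79.7% |
| 10% | 1% | √(4 + 0.10×1) = 2.02% | 79.2% |
| 10% | 2% | √(4 + 0.10×4) = 2.10% | 76.3% |
| 20% | 3% | √(4 + 0.20×9) = 2.41% | 64.5% |

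The last row takes the worst value of both inputs together. At 58 per arm, the 10% and 2% row gives 72.1%.

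**Step 3: bias from unmasked follow-up reading.** Suppose there is no true effect and knowledge of the arm shifts the between-arm difference by b points. The standard error is 2 × √(2/64) = 0.354, the noncentrality is b/0.354, and the critical value on 126 degrees of freedom is 1.979.

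| Assumed shift b | Noncentrality | Two-sided type I error |
|---|---|---|
| 0 | 0 | 5.0% |
| 0.1 | 0.28 | 5.9% |
| 0.2 | 0.57 | 8.7% |
| 0.25 | 0.71 | 10.8% |
| 0.5 | 1.41 | 28.9% |

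The documents give no value for b. The table shows how sensitive the test would be to a shift; it does not estimate one.

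**The case against.** The case on the other side is substantial.

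- **A reader might infer that scans are read locally by staff who know the arm.** The documents do not say so. Section 7.3 covers only where scans are completed. Section 5.3 issues the allocation to the site coordinator, and nothing says imaging staff receive it. This stands: masking is not stated, but unmasked reading is not documented either.
- **A reader might infer that the endpoint is biased.** That is not shown. Baseline scans precede randomisation, and BMD is a number in g/cm² (5.6), not a graded judgement. Exposure is confined to week 48, week 96 and any re-analysis of baseline. The documents support a risk of bias and no more.
- **A reader might infer that different machines at different sites are the problem.** Stable proportional calibration differences between sites cancel in percent change. Only a change within a woman matters, and it costs precision rather than validity because it is not expected to differ by arm.
- **The power losses rest wholly on assumptions.** At the low end the loss is about half a point, less than the plan's own dropout costs. The 2% SD comes from studies of observed BMD change, so it already contains measurement error and may include some scanner changes; adding more could double count.
- **Some protection is implied.** Women appear to stay at one site, the referring Toronto clinic sends its participants to a single centre (2.0), and personnel are trained on study procedures (12.1). The Operations Manual may say more, although the protocol does not point to it for DXA.

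These points limit the size of the claim. They do not supply the missing masking or scanner rule.

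**Conclusion.** The gap holds in limited form. For a locally acquired primary endpoint in an open-label trial, the plan does not say who reads the scans, mask follow-up acquisition or analysis, or keep each woman on one scanner.

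Neither risk can be sized from the documents. Under the assumptions above, scanner changes would cost between half a point of power and, in the worst case examined, about 16 points (80.1% to 64.5%); the middle case costs about 4 (80.1% to 76.3%). An assumed 0.2-point shift, one fifth of the target difference, would raise type I error to about 8.7%. Nothing here shows that the sample size is wrong or that the result would be invalid. This is a cheap improvement: simple steps reduce both risks, and none needs central reading.

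**What to change.** Add to section 7.3:

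1. DXA requests do not state the arm or the tenofovir regimen, and the existing local staff who acquire and analyse the scans are not told the arm.
2. Each woman's baseline, week-48 and week-96 scans are done on the same scanner where possible. All her scans are analysed with the same software version; if the software is upgraded, earlier scans are re-analysed masked to arm.
3. Scanner ID and software version are recorded on the CRF. All women stay in the primary analysis, and a sensitivity analysis adjusts for, or excludes, those whose scanner changed. Exclusion conditions on a post-randomisation event, so it should not replace the primary analysis.

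The cost is protocol wording, a revised request form, two CRF items and one sensitivity analysis. No extra scans or staff are needed, and the planned 128 does not change. The downsides are occasional rebooking or re-analysis, and imperfect masking, since a participant can disclose her arm. If sites already work this way, writing it down makes it checkable.
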